**Table ITSA.6.1 Treatment and Age Group Used in TFLs**

Study Treatment Name	Treatment order in TFL
LY900014	1
Humalog	2
Age Group Name	Age Group Order in TFL
Children	1
Adolescents	2
Adults	3

Abbreviation: TFL = Table, Figure, and Listing.

## 6.2. Demographics and Patient Disposition

Patient disposition will be listed. The demographic variables age, sex, race, ethnicity, hip and waist circumference, body weight, height, and body mass index will be summarised by age group and listed. In addition, screening HbA1c, previous insulin therapy (basal and prandial), insulin administration method (CSII or MDI) at screening, and duration of T1DM will be summarised and listed.

Alcohol consumption will be reported in the SDTMs in units of alcohol and will be converted to grams for the TFLs, where 1 unit is equal to 8 grams of pure alcohol.

## 6.3. Pharmacokinetic Analysis

### 6.3.1. Pharmacokinetic Parameter Estimation

Patients who receive at least 1 dose of study drug and have measurable insulin lispro concentrations will be included in the PK analysis dataset. The post-intervention glucose data will not be included in the PK analyses.

Pharmacokinetic analyses will be conducted using standard noncompartmental methods of analysis CCI and CCI software CCI on a computer that meets or exceeds the minimum system requirements for these programs. The version of any software used for the analysis will be documented and the program will meet the Lilly requirements of software validation. It is possible that other validated equivalent PK software programs may be utilised if appropriate, warranted, and approved by global PK management.

Free serum insulin lispro concentrations will be used to calculate several PK parameters, including early 50%  $t_{max}$ , time to late half-maximal drug concentration (late 50%  $t_{max}$ ), maximum observed drug concentration ( $C_{max}$ ), time of maximum observed drug concentration ( $t_{max}$ ), half-life ( $t_{1/2}$ ), and area under the plasma concentration time curve (AUC) from time zero to the last recorded time [ $AUC_{(0-tlast)}$ ], AUC from time zero to 30 minutes [ $AUC_{(0-30min)}$ ], AUC from time zero to 1 hour [ $AUC_{(0-1h)}$ ], AUC from time zero to 7 hours [ $AUC_{(0-7h)}$ ], and AUC from time zero to infinity [ $AUC_{(0-\infty)}$ ]. Other parameters may be calculated as deemed appropriate. Additional partial AUCs may be computed as necessary.

Although attempts will be made to adhere to the scheduled collection times, it is recognised that situations arise that may compromise the scheduled times. Parameters will be individually calculated for each patient based on actual collection times and presented by summary statistics and presented by each age group and treatment.

[figure not shown]
Study results may be pooled with the results of other studies for population PK analysis purposes to avoid issues with post hoc analyses and incomplete disclosures of analyses.

## 6.4. Glucodynamic Analyses

### 6.4.1. Glucodynamic Parameter Estimation

Patients who receive at least 1 dose of study drug and have completed at least 1 MMTT procedure will be included in the analysis set for the GD analyses. The post-intervention glucose data will not be included in the GD analyses.

Data will be analysed for the patients during each MMTT. The change from baseline values (the average of -30, -15, and 0 minutes represented as the 0-hour time point following the start of the MMTT) for each patient will be calculated. Mean change from baseline is the mean of all individual patients' change from baseline values. Each individual change from baseline will be calculated by subtracting the individual patient's baseline value from the value at the time point. The area under the baseline subtracted glucose concentration versus time curve ( $\Delta AUC$ ) from time 0 to 2 hours postmeal ( $\Delta AUC_{[0-2h]}$ ) and  $\Delta AUC$  from time 0 to 5 hours postmeal ( $\Delta AUC_{[0-5h]}$ ) will be calculated. In addition, the change from baseline maximum glucose observed during the 5 hours postmeal and change from baseline 1 hour glucose and 2 hour glucose after the start of the meal will be calculated. Other partial  $\Delta AUC$ s may be calculated, as deemed appropriate.

Parameters will be individually calculated for each patient and presented by summary statistics for each age group and treatment.

### **6.4.2. Glucodynamic Statistical Inference**

The population for GD statistical analyses is defined in Section 6.1. The GD parameters will be summarized by treatment and age group for each part of the study.

The GD parameters on the original scale (not log transformed) will be analysed using the same model used for PK parameters. Least-squares means, treatment differences in LSmeans, and the corresponding 95% CIs for the treatment differences will be estimated from the model. The treatment ratios and 95% CIs for the ratios will be calculated using Fieller's theorem.

The above analyses may be repeated for the patients who complete at least 1 treatment period for the MMTT.

An exploratory analysis on the interaction between treatment and age group will be evaluated for all GD parameters using the same statistical model used for treatment comparison. This test will be used to compare whether the LY900014 versus Humalog treatment effect is similar among all 3 age groups. The interaction effects will be evaluated using a significance level of 0.10.

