5.1.1.1. Inpatient Procedures for Part A

[figure not shown]
On the day before each MMTT day (i.e., Day -1 in each of the 2 periods), patients will arrive at the study site in the early evening (approximately 05:00 PM). The patient's short-acting insulin will be administered before the start of a standardised dinner. Before the start of a run-in period, the cannulation of the vein will be performed. At the start of the run-in period, patients entering the study on CSII therapy will suspend all insulin delivery and disconnect tubing from the infusion site.

Start of the run-in period will occur following the evening meal (approximately at 09:00 or 10:00 PM). The run-in period will start with a variable IV infusion of glucose (5% dextrose solution) or RHI to reach a target glucose level of 135 ± 25 mg/dL (7.5 ± 1.4 mmol/L). If this target glucose level is not attained before 11:00 AM on Day 1, MMTT will be halted and may be performed on a separate visit; an MMTT can only be rescheduled (up to 7 days) once for each study period. During the run-in period, blood glucose concentrations will be monitored at a minimum of 30- to 60-minute intervals (see Sections 7.4.1 and 9.6.1).

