10.1. Sample Size Determination

The number of patients needed to complete either Part A or Part B of this study was pre-set to 12 in each age group (6 to <12 years, 12 to <18 years, and 18 to <65 years). Twelve completing patients in each age group will provide approximately 90% power to demonstrate 60% increase in the insulin lispro area under the plasma concentration-time curve from time zero to 30 minutes (AUC[0-30min]) between LY900014 and Humalog within each age group. The sample size will also provide greater than 85% power to demonstrate 30% reduction in time to early half-maximal drug concentration (early 50% t_{max}). The estimated standard deviation of within-subject difference on the log scale is 0.45 for AUC(0-30min) and 0.35 for early 50% t_{max} , according to an analysis of internal Lilly data and external published paediatric studies. Testing will be done at an alpha level of 0.05 with a 2-sided confidence interval (CI).

Approximately 45 patients (approximately 15 patients in each age group) may be enrolled in the study to ensure approximately 36 patients complete both inpatient periods in both parts of the study. If patients complete Part A but decline participation in Part B or drop out from Part A, additional patients may be enrolled to ensure at least 36 patients complete Part B of the study.

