### 5.2. Determination of Sample Size

The number of patients needed to complete either Part A or Part B of this study was pre-set to 12 in each age group (6 to <12 years, 12 to <18 years, and 18 to <65 years). Twelve completing patients in each age group will provide approximately 90% power to demonstrate 60% increase in the insulin lispro area under the plasma concentration-time curve from time zero to 30 minutes ( $AUC_{[0-30min]}$ ) between LY900014 and Humalog within each age group. The sample size will also provide greater than 85% power to demonstrate 30% reduction in time to early half-maximal drug concentration (early 50%  $t_{max}$ ). The estimated standard deviation of within-subject difference on the log scale is 0.45 for  $AUC_{(0-30min)}$  and 0.35 for early 50%  $t_{max}$ , according to an analysis of internal Lilly data and external published paediatric studies. Testing will be done at an alpha level of 0.05 with a 2-sided confidence interval (CI).

Approximately 45 patients (approximately 15 patients in each age group) may be enrolled in the study to ensure approximately 36 patients complete both inpatient periods (i.e., 12 completers in each age group) for both parts of the study. If patients complete Part A but decline participation

in Part B or drop out from Part A, additional patients may be enrolled to ensure at least 36 patients complete Part B of the study.

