## 6. A Priori Statistical Methods

### 6.1. General Considerations

This SAP supersedes the statistical considerations identified in the protocol; where considerations are substantially different, they will be so identified. Data listings, summaries, and analyses will be performed by Covance Early Clinical (EC) Biometrics. If additional analyses are required to supplement the planned analyses described in this SAP, they may be performed and will be identified in the clinical study report (CSR). Any substantial deviations from this SAP will be agreed upon between Eli Lilly and Company and Covance EC Biometrics and identified in the CSR. Any minor deviations from the Tables, Figures, and Listings (TFLs) may not be documented in the CSR.

The analyses for Part A and Part B of the study will be conducted separately using similar statistical methods. Treatment comparisons between LY900014 and Humalog will be conducted at an alpha level of 0.05 with a 2-sided CI within each age group for each part of study.

The age groups used in the PK and GD analyses will be determined by the age of the patient at initial screening. For patients who participated in both parts of the study, the age at screening of Part A will be used in the analyses for both parts. For patients newly enrolled for Part B only, the age at screening of Part B will be used.

The analysis populations are defined for each study part separately. Primary statistical analyses for PK parameters will be conducted on the set of patients who complete both treatment periods with an identical bolus insulin dose for the MMTTs and have measurable insulin lispro concentrations within each part of the study. Supportive analyses may be done on the key parameters for the patients who complete at least 1 treatment period and have measurable insulin lispro concentrations within each part of the study.

Primary statistical analyses for GD parameters will be conducted on the set of patients who complete both treatment periods with an identical bolus insulin dose for the MMTTs within each part of the study. Supportive analyses may be done on the key parameters for the patients who complete at least 1 treatment period for the MMTT within each part of the study.

The post-intervention glucose samples will be collected in the database; however, the post-intervention glucose data will be excluded from PK and GD analyses.

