Safety analyses will be conducted for the set of patients receiving at least 1 dose of the study drug, whether or not they completed all protocol requirements.

All protocol deviations that occur during the study will be considered for their severity/impact and will be taken into consideration when patients are assigned to analysis populations.

Summary statistics (including number of patients, mean, standard deviation or standard error, minimum, and maximum) will be presented for continuous variables. Data from all 3 age groups will be pooled and analysed by a linear mixed-effect model for continuous variables unless otherwise stated in the succeeding subsections. The model will include treatment, sequence, period, age group, and the interaction of treatment and age group as fixed effects and patient

within sequence as a random effect. The primary comparison between LY900014 and Humalog for each age group will be based on the treatment difference or ratio of the given age group from the model.

For categorical data, frequency count and percentages will be presented in the summary table.

Data listings will be provided for all patients up to the point of withdrawal, with any patients excluded from the relevant population highlighted, using all data that are databased. Summary statistics and statistical analyses will generally only be performed for patients included in the relevant analysis population. For the calculation of summary statistics and statistical analysis, unrounded data will be used.

For weight and other clinical lab tests (based on data availability), mean change from baseline is the mean of all individual patients' change from baseline values. Each individual change from baseline will be calculated by subtracting the individual patient's baseline value from the value at the time point. The individual patient's change from baseline values will be used to calculate the mean change from baseline using CCI [REDACTED]

Additional exploratory analyses of the data will be conducted as deemed appropriate.

Data analysis will be performed using CCI [REDACTED] or greater.

Table ITSA.6.1 is a list of the study treatment and age group names that will be used in the statistical TFLs.

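### The glucodynamic model uses baseline glucose only by subtraction; prespecifying it as a within-patient covariate in Part A could narrow the ΔAUC intervals at little cost

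*SAP*

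**What the plan says.** SAP section 6.4.2 carries the pharmacokinetic model over to the glucodynamic parameters: "The GD parameters on the original scale (not log transformed) will be analysed using the same model used for PK parameters". SAP section 6.1 lists its terms: "The model will include treatment, sequence, period, age group, and the interaction of treatment and age group as fixed effects", with patient within sequence as a random effect. Protocol sections 10.3, 10.3.2.2 and 10.3.3.2 agree. A redacted block follows the model text in SAP section 6.3.2. Its content is unknown, but the readable text gives a full list of terms, and baseline glucose is not among them.

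Baseline enters in one place only. SAP section 6.4.1 and Protocol section 10.3.3.1 average the readings at -30, -15 and 0 minutes of each meal test and subtract that mean from the later values to form ΔAUC.

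The design also controls baseline. In the overnight run-in (Protocol section 5.1.1.1), intravenous dextrose or regular human insulin is given "to reach a target glucose level of 135 ± 25 mg/dL (7.5 ± 1.4 mmol/L"), and glucose must be on target and stable without intervention for at least 20 minutes before the meal. Protocol section 5.4 gives the purpose: similar premeal glucose and a less variable response.

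On inference, SAP section 6.1 states: "Treatment comparisons between LY900014 and Humalog will be conducted at an alpha level of 0.05 with a 2-sided CI within each age group". According to SAP section 5.2, the number of completers "was pre-set to 12 in each age group".

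**The concern.** ΔAUC(0-5h) contains minus 5 h times the period's baseline, and ΔAUC(0-2h) contains minus 2 h times it. Subtraction is the efficient use of baseline only if a start 1 mg/dL higher raises mean postmeal glucose by 1 mg/dL over the whole window.

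There are reasons to doubt that here. Baseline is partly imposed by a variable infusion. The -30 minute reading can precede the required 20 stable minutes. The readings come from a point-of-care meter (Protocol section 9.6.1), so the baseline carries error. A weight-based insulin dose and a meal then act for up to 5 hours.

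If the true within-patient slope is below 1, subtraction over-corrects and leaves removable noise in the between-period difference. At stake is the width of the intervals for two secondary endpoints, with 12 completers per age group. The Part A results are meant to support regulatory submission and future study design (SAP section 6.6).

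**Working it through.** **The plan's own figures.** The only stated power is for pharmacokinetics. A paired t-test with 12 patients and a two-sided alpha of 0.05 uses noncentrality |ln ratio| × √12 / SD.
- AUC(0-30min): ln 1.60 = 0.470 and SD 0.45 give 0.470 × 3.464 / 0.45 = 3.62. Power is 90.8% (11 df) or 90.2% (10 df), against about 90% stated.
- Early 50% t_max: |ln 0.70| = 0.357 and SD 0.35 give 3.53. Power is 89.4% or 88.8%, against more than 85% stated.

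Both reproduce. No SD, correlation or power is stated for ΔAUC, so the rest uses assumed inputs.

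**Assumptions.**
- Within-patient baseline SD is 12.5 mg/dL per period (±25 taken as two SDs).
- Meter error SD is 6 mg/dL per reading. Averaging three readings leaves an error variance of 36/3 = 12.
- The other SD of the between-period difference, S, is 100 to 250 mg·h/dL for 0-5h and 60 to 120 for 0-2h.
- The within-patient slope b of mean postmeal glucose on true baseline is 0 to 1.

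**Formulas.** For between-period differences, the true baseline variance is 2 × 12.5² = 312.5 and the error variance is 2 × 12 = 24, so the observed baseline variance is 336.5. With h = 2 or 5 hours:
- Cov(ΔAUC, baseline) = h[(b−1) × 312.5 − 24]
- Var(ΔAUC) = h²[(b−1)² × 312.5 + 24] + S²
- ρ² = Cov² / [336.5 × Var(ΔAUC)]
- Residual df: 36 − 3 age-specific treatment effects − 1 period effect = 32, and 31 with the covariate.
- Variance ratio (adjusted/planned) ≈ (1 − ρ²)(1 + 1/30), where 1/30 is the approximate cost of estimating the slope.
- Width ratio = √(variance ratio) × 2.0395/2.0369, the two t quantiles.

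**Example (h = 5, S = 150, b = 0.3).** Cov = 5 × (−218.75 − 24) = −1213.75. Var = 25 × (153.125 + 24) + 22500 = 26928. ρ² = 1213.75² / (336.5 × 26928) = 0.163. The variance ratio is 0.837 × 1.033 = 0.865 and the width ratio is 0.93. Simulation of this design (36 patients, 3,000 runs per setting) gives the same values.

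**Width ratio over the range.**

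| Endpoint | S (mg·h/dL) | b = 0 | b = 0.3 | b = 0.6 | b = 1 |
|---|---|---|---|---|---|
| ΔAUC(0-5h) | 100 | 0.75 | 0.85 | 0.94 | 1.02 |
| ΔAUC(0-5h) | 150 | 0.87 | 0.93 | 0.98 | 1.02 |
| ΔAUC(0-5h) | 250 | 0.96 | 0.98 | 1.00 | 1.02 |
| ΔAUC(0-2h) | 60 | 0.87 | 0.93 | 0.98 | 1.02 |
| ΔAUC(0-2h) | 120 | 0.97 | 0.99 | 1.01 | 1.02 |

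The rows for 0-5h at 150 and 0-2h at 60 coincide because 150/5 = 60/2. The smaller gain for 0-2h therefore reflects the assumed SD range.

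**Break-even.** Setting the width ratio to 1 gives ρ² ≈ 0.035, so |ρ| is about 0.2. Below that, adjustment gains nothing.

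**Other assumptions.** With no separate meter error, a baseline SD of 12.5 to 14.4 (14.4 = 50/√12, uniform over 110 to 160) and S of 150 to 300 for 0-5h or 60 to 120 for 0-2h, |ρ| runs from 0 at b = 1 to 0.56 at b = 0. The width ratio then runs from 1.02 to √[(1 − 0.56²) × 31/30] × 1.001 = 0.84.

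**The case against.** The strongest reply is that the plan already handles baseline twice: the run-in narrows it, and ΔAUC subtracts each period's own value. A reader might infer that baseline is ignored, or that chance imbalance between treatments goes uncorrected. The documents do not support that. Subtraction corrects imbalance, though possibly by too much. Nor is the 50 mg/dL between the ends of the target window a typical difference between a patient's two periods; it is the extreme.

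A second reply is that the gain is conditional. A reader might take the loss of precision as established, but nothing in the documents fixes the correlation or the SD. The 0.75 needs slope 0 together with the smallest SD. This stands, and it limits the claim to intervals that may be wider than needed.

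A third reply concerns Part B, and it changes the remedy. Under Protocol section 5.1.2.1 the reservoir holds the randomised insulin from the evening before and runs at a low basal rate until 2 hours before the scheduled meal test. SAP section 6.5.1 itself places Part B dosing at insertion of the infusion set with study treatment. The Part B baseline is therefore not strictly pre-treatment, and adjusting for it could change what the contrast means. Subtraction uses the same baseline, so the planned analysis is not free of this either, but it is a reason not to make the adjusted model primary there.

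Finally, these endpoints are secondary and unpowered, and the SAP already allows exploratory analyses. That is true, but an adjustment chosen after treatment-level results are seen carries less weight than a prespecified one.

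**Conclusion.** The point holds as an available improvement in precision, not as an error. The readable glucodynamic model has no baseline covariate, and subtraction fixes the slope at 1. Under the stated assumptions, adjustment changes the interval width for ΔAUC(0-5h) by between about 25% narrower and 2% wider, with about 7% narrower in the middle case (variance ratio about 0.86). For ΔAUC(0-2h) the range is about 13% narrower to 2% wider. The gain requires a within-patient correlation of at least about 0.2 between ΔAUC and baseline after subtraction.

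The omission is certain; its size is not. It would be wrong to conclude that the planned comparison is biased or invalid, or that any stated figure is incorrect: the two stated pharmacokinetic powers reproduce, and none is stated for ΔAUC.

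**What to change.** In SAP section 6.4.2, prespecify for Part A a glucodynamic model with two added terms: the patient's mean baseline glucose over both periods, and the period's deviation from that mean. Entering the raw period baseline alone would blend within- and between-patient slopes; the deviation term gives the treatment contrast its within-patient slope. State that LSmeans and Fieller ratios are evaluated at the overall mean baseline and zero deviation, because ratios of adjusted means depend on where they are taken. Keep the unadjusted model as a sensitivity analysis.

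For Part B, keep the planned model as primary and prespecify the adjusted one as a sensitivity analysis only, giving the overnight exposure to randomised insulin as the reason.

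The cost is a few sentences in the SAP and no new data. The treatment contrast loses about 1 degree of freedom, and its intervals would be up to about 2% wider if the slope is in fact 1.

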## **6.5. Safety and Tolerability Assessments**

### **6.5.1. Adverse Events**

Where changes in severity are recorded in the Case Report Form (CRF), each separate severity of the adverse event (AE) will be reported in the listings, only the most severe will be used in the summary tables. A pre-existing condition is defined as an AE that starts before the patient has provided written informed consent and is ongoing at consent. A nontreatment-emergent AE is defined as an AE that starts after informed consent but prior to dosing (prandial MMTT dosing for Part A and infusion set with study treatment inserted for Part B). A treatment-emergent AE is defined as an AE that occurs postdose or that is present prior to the first dose and becomes more severe postdose.

Treatment-emergent AEs will be summarized by treatment, age group, severity, and relationship to the study drug. The frequency (the number of AEs, the number of patients experiencing an AE, and the percentage of patients experiencing an AE) of treatment-emergent AEs will be summarized by treatment, age group, Medical Dictionary for Regulatory Activities version 20.0 system organ class and preferred term. The summary and frequency AE tables will be presented for all causalities and those considered related to the study drug.

All AEs will be listed. Any serious AEs will be tabulated.

